11.2 Baseline Evaluations

The following will be performed within 8 weeks prior to administration of porfimer sodium:

- Informed consent: Must be completed prior to receiving any study-related procedures
- Medical history
- Physical examination including vital signs (i.e., temperature, heart rate, respiratory rate, blood pressure, body weight, height, and pain assessment using a verbal score of 0 10) *
- Hematology (i.e., complete blood count (CBC) with auto differential, absolute neutrophil count (ANC), and platelets) *, **
- Chemistry (i.e., AST, ALT, total bilirubin, alkaline phosphatase, creatinine, potassium, glucose, and calcium) *
- Pregnancy test (urine) in females of childbearing potential **
- ECOG Performance Status **
- UW OoLO v4 #
- Standard imaging for patients with HNC (i.e., CT and/or MRI) *, at least 10 business days prior to the scheduled I-PDT #
- Pretreatment planning #
- Concomitant Medications (including narcotic and nonnarcotic analgesics) **

**These will be done prior to later 2nd and 3rd later I-PDT sessions (if later I-PDT sessions are required per treating physician's discretion per Section 10.4). Height does not need to be reassessed for later possible I-PDT sessions. If later I-PDT courses are deemed necessary, previous study treatment adverse events will be reviewed before the start of next I-PDT course.

Performed as per PI discretion if 2nd and 3rd I-PDT courses are deemed necessary as per Section 10.4.

^{*}These are standard of care and may be used for baseline evaluation if performed before informed consent but within 4 weeks of porfimer sodium and can be used for the pretreatment planning.

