11.5 Evaluations Performed at 1st Post-Operative Clinic Visit

This visit will be scheduled 1 to 4 weeks post I-PDT and will include:

- Physical examination, including vital signs (i.e., temperature, heart rate, respiratory rate, blood pressure, body weight, and pain assessment using a verbal score of 0-10)
- Hematology (i.e., CBC (with auto differential), ANC, and platelets)
- Chemistry (i.e., AST, ALT, total bilirubin, alkaline phosphatase, creatinine, potassium, glucose, and calcium)
- ECOG Performance Status
- Adverse events
- UW QoLQ v4
- Research blood draws (Optional) #

Performed as per PI discretion if later I-PDT courses are deemed necessary as per Section 10.4.

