19.6 Adverse Events

The frequency of toxicities will be tabulated by grade across all dose levels and cycles. All subjects who receive any study treatment will be considered evaluable for toxicity.

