Appendix D Schedule of Procedures and Observations if Only I-PDT Course is Necessary

Evaluation	Baseline ¹	Pre- Operative	Day of Treatment	Day 1 Post Treatment	1-week Post- treatment	Optional I-PDT Course 2 Within 2-3 Weeks of Day 0 ¹⁷	Clinic Visit ^{2,2a}	30- Day Post I- PDT ¹⁴	Optional I-PDT Treatment additional 2 or 3 At least 6 Weeks after last I-PDT Session ¹⁸	Follow- Up
Informed Consent	X									
Medical History	X								X	
Physical Exam/ Vital signs & pain assessment using a verbal score 0-10 ³	X				X		X	X	X	X
Hematology ⁴ and Chemistry ⁵	X				X		X	X	X	
Research Blood Draws ⁶			X		X		X	X	X	
Pregnancy Test (Urine)	X								X	
ECOG Performance Status	X		X		X		X	X	X	X
UW-QoLQ v. 4 ¹⁵	X				X		X	X	X	X
Standard Imaging of the head and neck with CT or MRI, for RECIST v11.1	X ⁷								X	X8
Treatment planning	X								X	
Porfimer Sodium administration and Vital Signs		X ⁹							X	
Intraoperative Ultrasound			X						X	
If possible, intraoperative CT or other clinically approved radiological imaging			X^{10}			X ¹⁰			X^{10}	
Interstitial PDT (I-PDT) 16			X^{11}			X ¹¹			X ¹¹	
Concomitant Medications	X ¹²		X							
Adverse Events ¹³			X		X		X	X		

Notes:

- * The I-PDT procedure is termed a "course".
 - 1. Performed within 8 weeks prior to porfimer sodium.
 - Performed at Day 1 of SOC therapy.
 If later 2nd and 3rd I-PDT courses are deemed necessary per the physician (see Section 10.4), please refer to Appendix D 1 for treatment, procedure, and test scheduling.
 - 3. Temperature, heart rate, respiratory rate, blood pressure, body weight and, height, Height collected at baseline only. Refer to Section 11.2.
 - 4. Hematology (i.e., CBC (with auto differential), ANC, and platelets). Refer to Section 11.2.
 - 5. Chemistry (i.e., AST, ALT, total bilirubin, alkaline phosphatase, creatinine, potassium, glucose, and calcium). Refer to Section 11.2.
 - 6. This is optional. Refer to immune markers Section 11.8 (1, 10 mL green-top tube).
 - 7. Standard tumor staging performed within 4 weeks, and at least 14 business days prior to I-PDT. If possible, the imaging will include temporary fiducial markers that will be affixed to skin. Refer to Section 11.2.
 - 8. CT scans at 10 to 12 weeks post SOC therapy and as clinically indicated following the NCNN 2018 guidelines.
 - 9. Infusion will occur 48 hours ± 8 h prior to illumination. Vitals are to be taken immediately after injection and after 15 minutes.

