 - 10. If possible, intraoperative CT (such as O arm) or another radiological imaging (e.g. C-arm) will be used to image the catheters in the tumor.
 - 11. Refer to Section 10.2.1.
 - 12. Medications ongoing within 1 week prior to porfimer sodium injection.
 - 13. AE reporting period will be for 30 days \pm 2 days post first SOC treatment.
 - 14. First SOC treatment day of I-PDT day if no therapeutic SOC treatment is administered.
 - 15. Refer to Section 11.6f patient doesn't come in or quality of life is missed, may be done via telephone.
 - 16. In the event that the tumor size is such that treating the entire tumor could cause a health risk to the patient, the current I-PDT course will be broken up into session/s. We will illuminate one part of the tumor on the day of I-PDT and another part/s of the tumor in additional I-PDT session/s within 14 days after the initial I-PDT session, at the discretion of the treating physician. If

- an I-PDT course is broken up into I-PDT sessions, the I-PDT dosage for each session will remain the same as though sessions were not broken up as dosing is dependent on number of fibers received per session. The patient will not need to receive additional doses of porfimer sodium if having additional I-PDT sessions within 14 days after the previous I-PDT session as porfimer sodium is expected to be in the tumor for at least 30 days.
- 17. Another (one or two, total of three) laser light treatment(s) only (no additional drug) within 2-3 weeks of the initial administration of Photofrin.
- 18. Patient may receive a second complete I-PDT treatment that will include drug and light administration. It will be at the discretion of the treating physician to administer this additional treatment. Another CT (charged to the study if it is not SoC) will be done, and all tests will be conducted before and after additional treatment, according to the same schedule parameters as the initial treatment.

Appendix D 1 Schedule of Procedures and Observations (Only for Dose Escalation later I-PDT Sessions if Deemed Necessary by Physician)**

Evaluation	Repeat of Initial Tests and Procedures ^A	Pre- Operative	Day of Treatment	1-week Post- treatment	Clinic Visit	Post- Treatment	Follow- Up
Physical Exam/ Vital signs ^B & pain assessment using a verbal score 0-10	X			X	X	X	X
Hematology ^C and Chemistry ^D	X			X	X	X	
Research Blood Draws ^E			X	X	X	X	X
Pregnancy Test (Urine)	X						
ECOG Performance Status	X		X	X	X	X	X
UW-QoLQ v. 4 ^p	X			X	X	X	X

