Fresh Tissue Tumor Biopsy ^F	X			X			
Standard Imaging of the head and neck with CT or MRI ^G	XH						XI
Treatment planning	X						
Porfimer Sodium administration and Vital Signs		X^{J}					
Intraoperative Ultrasound ^Q			X				
If possible, intraoperative CT or other clinically approved radiological imaging			X ^K				
Interstitial PDT (I-PDT)			$X^{L, Li}$				
Concomitant Medications	X ^M		X				
Standard of care (SoC) chemotherapy, targeted therapy or potentially immunotherapy as first line palliative care treatment options					X ^N		
Adverse Events ^O	X ^{Oi}		X	X	X	X	

Notes:

^{*} The I-PDT procedure is termed a "course". As per later Section 10.4, study participants may have up to 3 I-PDT courses per physician's discretion, at least 30 days from the previous illumination procedure.

- ** NOTE: 2nd and 3rd I-PDT courses are per the physician's discretion as per Section 10.4, 2nd and 3rd I-PDT courses are not required for all study participants. If it is decided participants should receive all 3 I-PDT courses, items from "Repeat of Initial Tests and Procedures" until the completion of I-week Post treatment" are completed twice before the Clinic Visit and start of Standard of Care chemotherapy.
 - A. Performed within 4 weeks prior to 2nd and 3rd I-PDT courses. Since there may be up to three I-PDT courses, at least 30 days apart (see Section 10.4) per the physician's discretion, the initial procedures, exams, or tests may be completed up to two more times based on the individual participant's study treatment regimen. Research blood draws, standard imaging of head and neck with CT or MRI, and treatment planning for later I-PDT courses are per physician's discretion.
 - B. Temperature, heart rate, respiratory rate, blood pressure, and body weight. Refer to Section 11.2.
 - C. Hematology (i.e., CBC (with auto differential), ANC, and platelets). Refer to Section 11.2.
 - D. Chemistry (i.e., AST, ALT, total bilirubin, alkaline phosphatase, creatinine, potassium, glucose, and calcium). Refer to Section 11.2.
 - E. This is optional. Research blood draws for any 2nd and 3rd I-PDT courses (all timepoints) are per the physician's discretion. Refer to immune markers Section 11.8 (1 green top tube).

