 - F. If required per physician's discretion, standard tumor staging performed within 4 weeks, and at least 14 business days prior to following I-PDT. If possible, the imaging will include temporary fiducial markers that will be affixed to skin. Refer to Section 11.2.
 - G. CT scans at 10 to 12 weeks post I-PDT and as clinically indicated following the NCNN 2018 guidelines.
 - H. If tumor results determine porfimer sodium infusion is needed for later 2nd and 3rd I-PDT sessions, infusion will occur 48 hours ±8 h prior to illumination. Vitals are to be taken immediately after injection and after 15 minutes.
 - I. If possible, intraoperative CT (such as O arm) or another radiological imaging (e.g. C-arm) will be used to image the catheters in the tumor.
 - J. Refer to Section 10.2.1.
 - K. Medications ongoing within 1 week prior to illumination.
 - L. Refer to Section 10.2.1.
 - Li. The later 2nd and 3rd I-PDT study treatments total as per the physician's discretion are at least 30 days apart from each other (see Section 10.4). For additional I-PDT treatments that are 30 days from the previous that require an additional dosage of porfimer sodium the porfimer sodium (2mg/kg) is administered 48 hours prior to illumination.
 - M. AE reporting period will be for 30 days \pm 2 days post first SOC treatment.
 - Oi. Since there may be up to three I-PDT courses, at least 30 days apart (see Section 10.4), per the physician's discretion, adverse events review of previous study treatments are reviewed prior of the next additional I-PDT.
 - N. In Phase 1, patients are off treatment/on follow up as clinically indicated 30 days after the last I-PDT.
 - O. Refer to Section 11.6 if patient doesn't come in or quality of life is missed, may be done via telephone.

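### Appendix D 1 and note 18 of Appendix D give conflicting safety-visit schedules after a repeat I-PDT course; under D 1 a non-final course gets fewer scheduled exams and laboratory tests (1 to 2 against 3)

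*Combined protocol and SAP*

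**What the plan says.** Section 10.4 allows up to three courses at least 30 days apart, at the physician's discretion. Appendix D 1 schedules the later ones. Its double-asterisk note says that, if all three are given, the items from the repeat work-up to the end of the 1-week visit "are completed twice before the Clinic Visit and start of Standard of Care chemotherapy".

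Note 18 of Appendix D, on an additional complete treatment with drug and light, says that "all tests will be conducted before and after additional treatment, according to the same schedule parameters as the initial treatment". The initial schedule in Appendix D includes a 1-week visit, a Clinic Visit and a 30-day visit, each with exam, laboratory tests and adverse events.

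The anchors of those visits add to the difficulty. The Clinic Visit is "Performed at Day 1 of SOC therapy", and the next note line sends participants with later courses to Appendix D 1. Note 14 ties the 30-day visit to the first standard-of-care day, or to the I-PDT day if no such treatment is given.

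There are other contacts between courses. Section 11.2 says that "previous study treatment adverse events will be reviewed before the start of next I-PDT course", and note Oi of Appendix D 1 repeats the requirement. Section 11.4 has an adverse-event check on each treatment day. Section 19.6 says: "The frequency of toxicities will be tabulated by grade across all dose levels and cycles".

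**The concern.** The two notes are competing instructions for the same participants, so what is done after a non-final course depends on which note the site reads. The cross-reference to Appendix D 1 makes the reduced schedule the likely default.

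The stake is the safety record, in a trial of at most 12 participants whose primary objective is safety. Laboratory abnormalities may cause no symptoms, so continuous adverse-event reporting under Section 17.3 does not fully replace a scheduled test. Section 10.3 also holds further I-PDT after a dose-limiting toxicity, so what is found after a non-final course bears on the next one. If toxicity were then set out by course, part of any difference could reflect how often exams and tests were scheduled.

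**Working it through.** No figure in the plan depends on this schedule, so the check is a count of scheduled contacts.

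**Inputs**
- Appendix D 1 marks for adverse events and ECOG: repeat work-up, treatment day, 1-week, Clinic Visit, Post-Treatment. For exam and laboratory tests: the same without the treatment day. The Follow-Up column is left out.
- Repeat work-up: within 4 weeks (28 days) before course 2 or 3 (Appendix D 1, note A).
- Gap between courses: at least 30 days (Section 10.4). The Appendix D column for additional treatment says at least 6 weeks (42 days).

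**Step 1: order of visits.** With three courses the repeat block runs 3 − 1 = 2 times, and only then come the Clinic Visit and Post-Treatment. Neither is scheduled between courses 2 and 3. Note 18 would require both there.

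**Step 2: count per course**

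| Row | Non-final course, D 1 | Last course, D 1 | Non-final course, note 18 visits added |
|---|---|---|---|
| Adverse events | 1-week + next work-up + next treatment day = 3 | 1-week + Clinic + Post-Treatment = 3 | 3 + 2 = 5 |
| ECOG | 3 | 3 | 5 |
| Exam, laboratory | 1-week + next work-up = 2 | 3 | 2 + 2 = 4 |

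**Step 3: timing of the work-up.** Earliest day after the previous course = gap − 28.
- Gap 30 days: 30 − 28 = day 2. The day-7 visit is 30 − 7 = 23 days before the next course, within the 28 allowed, so one sitting could serve as both. Exam and laboratory contacts are then 1 to 2, against 3.
- Gap 42 days: 42 − 28 = day 14. The two contacts are separate, but the second may fall after day 30.

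In both cases the number inside the first 30 days is 1 or 2. The 3 after the last course counts columns: Appendix D 1 gives no day for Post-Treatment.

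**Step 4: course 1.** Appendix D places the Clinic Visit and 30-day columns before the optional later treatment, which suggests that course 1 keeps them. Its notes anchor them to the start of standard of care and refer repeat-course participants to Appendix D 1, which covers only later courses. The text does not settle the matter.

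**Step 5: the back-up laboratory test.** In Section 11.2, as the text reads, hematology carries the repeat mark and chemistry does not. Appendix D 1 marks both.

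**Step 6: what a missing contact could cost.** The documents give no detection probability. Assume that a lasting abnormality is picked up with probability p at each of k independent contacts: P = 1 − (1 − p)^k.

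| p (assumed) | k = 1 | k = 2 | k = 3 |
|---|---|---|---|
| 0.3 | 0.30 | 0.51 | 0.657 |
| 0.5 | 0.50 | 0.75 | 0.875 |
| 0.9 | 0.90 | 0.99 | 0.999 |

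The shortfall against three contacts runs from 0.009 (p = 0.9, k = 2) to 0.375 (p = 0.5, k = 1) over these values.

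**The case against.** The best defence is that adverse events are not watched less closely after an earlier course. The pre-course review is required in two places, each treatment day has its own check, and reporting runs without a break to 30 days after the last intervention. The dose-limiting-toxicity window and the primary safety endpoint are both anchored to the final I-PDT day, the course that has every visit. Repeat courses are discretionary and the output is descriptive. This stands for the adverse-event row. It does not resolve the conflict between the notes or supply a dated exam and laboratory test after a non-final course.

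Three stronger readings are tempting but unsupported:

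- A reader might infer that Section 11.5 also conflicts with Appendix D 1. It says only that "This visit will be scheduled 1 to 4 weeks post I-PDT". The 1-week visit that D 1 keeps after every course falls in that window with the same safety content.
- A reader might infer that the toxicity table must show lower rates in earlier cycles. Section 19.6 can mean pooling over cycles, and it states no comparison between them.
- A reader might count only the dedicated post-treatment visits, 1 against 3, and treat the rest of each 30-day window as empty. That ignores the repeat work-up, which may fall inside it, and takes the loss of visits after course 1 as settled.

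**Conclusion.** The contradiction is real: when three courses are given, the Appendix D 1 note and note 18 of Appendix D cannot both be followed. Under D 1, adverse-event contacts are equal (3 against 3), and the shortfall is in exams and laboratory tests, 1 to 2 against 3. This rests on reading the columns as visits and the work-up window as written. It is clear for course 2 of three and ambiguous for course 1. The effect on recorded toxicity has no fixed size in the documents, and no sample size, error rate or dose decision is shown to change. The notes should still be corrected, because they are conflicting rules on safety assessments in a safety trial and the repair is cheap.

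**What to change.** Reconcile the double-asterisk note of Appendix D 1, notes 2, 14 and 18 of Appendix D, and the repeat marks in Section 11.2. Each course, including course 1, should have the same stated adverse-event, exam and laboratory assessments through day 30, dated from that course. The next pre-course work-up can count as the day-30 assessment when it falls at that time. State in Section 19.6 whether toxicity is pooled or tabulated per course. If the uneven schedule is kept, add that no comparison across cycles will be made.

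The cost is a schedule amendment and a sentence in Section 19.6. Where the work-up serves as the day-30 assessment, exam and laboratory contacts after a non-final course go from 2 to 3. That is one extra standard assessment per non-final course, so one or two per repeat-course participant (2 − 1 = 1 or 3 − 1 = 2). Where the work-up cannot serve, that course needs one more.

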Appendix E University of Washington Quality of Life Questionnaire

	Date:/ Subject ID#
	is questionnaire asks about your health and quality of life over the past seven days. Please wer all of the questions by checking one box for each question.
1.	Pain (Check one box:)
	I have no pain.
	There is mild pain not needing medication.
	I have moderate pain - requires regular medication (codeine or nonnarcotic).
	I have severe pain controlled only by narcotics.
	I have severe pain, not controlled by medication.
2.	Appearance (Check one box:)
	There is no change in my appearance.
	The change in my appearance is minor.
	My appearance bothers me but I remain active.
	I feel significantly disfigured and limit my activities due to my appearance.
	I cannot be with people due to my appearance.
3.	Activity (Check one box:)
	I am as active as I have ever been.
	There are times when I can't keep up my old pace, but not often.
	I am often tired and have slowed down my activities although I still get out.
	I don't go out because I don't have the strength.
	I am usually in bed or chair and don't leave home.
4.	Recreation (Check one box:)
	There are no limitations to recreation at home or away from home.
	There are a few things I can't do but I still get out and enjoy life.
	There are many times when I wish I could get out more, but I'm not up to it.
	There are severe limitations to what I can do, mostly I stay at home & watch TV.

Roswell Park Protocol No.: I 67918

I can't do anything enjoyable.5. Swallowing (Check one box:) I can swallow as well as ever. I cannot swallow certain solid foods. I can only swallow liquid food. I cannot swallow because it "goes down the wrong way" and chokes me. Chewing (Check one box:) I can chew as well as ever. I can eat soft solids but cannot chew some foods. I cannot even chew soft solids. Speech (Check one box:) My speech is the same as always. I have difficulty saying some words but I can be understood over the phone. Only my family and friends can understand me. I cannot be understood. Shoulder (Check one box:) I have no problem with my shoulder. My shoulder is stiff but it has not affected my activity or strength. Pain or weakness in my shoulder has caused me to change my work. I cannot work due to problems with my shoulder. Taste (Check one box:) I can taste food normally. I can taste most foods normally. I can taste some foods. I cannot taste any foods. 10. Saliva (Check one box:) My saliva is of normal consistency. I have less saliva than normal, but it is enough.

I have no saliva.

I have too little saliva.

13MAR2023; SRC 18SEP2023; IRB 15NOV2023

Roswell Park Protocol No.: I 67918

11. Mood (Check one box:

My mood is excellent and unaffected by my cancer.

My mood is generally good and only occasionally affected by my cancer.

I am neither in a good mood nor depressed about my cancer.

I am somewhat depressed about my cancer.

I am extremely depressed about my cancer.

12. Anxiety (Check one box:)

I am not anxious about my cancer.

I am a little anxious about my cancer.

I am anxious about my cancer.

I am very anxious about my cancer.

Which issues have been the most important to you during the past 7 days?

Check up to 3 boxes.

Pain Swallowing Taste

Appearance Chewing Saliva

Activity Speech Mood

Recreation Shoulder Anxiety

GENERAL QUESTIONS

Compared to the month before you developed cancer, how would you rate your health-related quality of life? (check one box:)

Much better

Somewhat better

About the same

Somewhat worse

Much worse

Roswell Park Protocol No.: I 67918

In general, would you say your health-related quality of life during the past 7 days has been: (check one box:)
Outstanding
Very good
Good
Fair
Poor
Very poor
Overall quality of life includes not only physical and mental health, but also many other factors, such as family, friends, spirituality, or personal leisure activities that are important to your enjoyment of life. Considering everything in your life that contributes to your personal well-being, rate your overall quality of life during the past 7 days. (Check one box:)
Outstanding
Very good
Good
Fair
Poor
Very poor
Please describe any other issues (medical or nonmedical) that are important to your quality of life and have not been adequately addressed by our questions (you may attach additional sheets if needed).
Signature
Printed name
Date

